5.4.8.3. Exploratory Efficacy Analyses

Overall survival, as well as the efficacy parameters based on iRECIST, will also be analyzed as the exploratory objectives.

The efficacy parameters based on iRECIST will also be analyzed as the exploratory objective.

Overall response rate (iORR) is measured by the percentage of patients who achieved a iCR or iPR as their best overall response (iBOR) out of all treated patients (safety population). The

iBOR is defined as the best response across all time point assessments based on RECIST 1.1 and iRECIST.

Progression-free survival (iPFS) should be the date of randomization (the date of first dose for single-arm study) to the date at which progression criteria are first met (that is, the date of first unconfirmed progression [iUPD]) provided that iUPD or a sequence of consecutive iUPDs is confirmed by a confirmed progression (iCPD), the iUPD followed by only iUPDs at subsequent assessments, no more tumor assessments, or to the death date from any cause in the absence of progressive disease. Patients known to be alive and without the iUPD as mentioned above as of the data inclusion cut-off date for a particular analysis will be censored at the time of the last adequate tumor assessment (a detailed iPFS event/censoring scheme is provided in the table below).

Table JZIA.5.3. Progression-Free Survival (iPFS) Event/Censoring Scheme

Situation ^a	Event/Censor	Date of Event or Censor
iUPD confirmed at next assessment (iCPD) or consecutive iUPD followed by an iCPD	Event	(First) iUPD date
iUPD followed by only iUPD at subsequent assessments and no further tumor assessment available.	Event	First iUPD date of the consecutive iUPDs
iUPD without subsequent assessment	Event	iUPD date
Death	Event	Death date if no iUPD date as in the above 3 situations before death.
No Death and no iUPD or iUPD is followed by iSD/iPR/iCR/	Censored	Date of last adequate tumor assessment per iRECIST, or date of randomization (first dose for single-arm study) (whichever is later) ^b
Confirmed iUPD (iCPD) or death reported after 2 scan intervals following the last adequate tumor scan	Censored	Date of last adequate tumor scan prior to confirmed iUPD (iCPD) or death
No baseline radiologic tumor assessment available	Censored	Date of randomization (first dose for single-arm study)

No adequate postbaseline tumor assessment available and death reported after 2 scan intervals following the first dose ^{b,c}	Censored	Date of randomization (first dose for single-arm study)
--	----------	---

Abbreviations: i = immune responses assigned using iRECIST; iCR = complete response; iPR = partial response; iSD = stable disease; iUPD=unconfirmed progression; iCPD = confirmed progression; iPFS = progression-free survival; RECIST = Response Evaluation Criteria in Solid Tumors; SAP = statistical analysis plan.

^a Symptomatic deterioration (that is, symptomatic progression that is not confirmed per iRECIST) will not be considered as tumor progression.

^b Adequate tumor assessment per iRECIST refers to an assessment with one of the following responses: iCR, iPR, iSD, iUPD, or iCPD.

^c Refer to the statistical analysis plan for the definition of 2 scan intervals, including any adjustment for scan window (new anticancer therapy in SAP).

Duration of response (iDoR) is defined as the time from the date measurement criteria for iCR or iPR (whichever is first recorded) are first met until the first date that disease is recurrent or objective progression (as assessed by investigators) is observed, or the date of death from any cause in the absence of objectively determined disease progression or recurrence. Patients known to be alive and without disease progression as of the data inclusion cut-off date for a particular analysis will be censored at the time of the last adequate tumor assessment. Duration of response will follow the same censoring scheme as iPFS. Duration of response will be analyzed for the treated patients who achieve iCR/iPR as the iBOR.

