8.1. Efficacy Assessments

Tumor assessments will be performed for each patient at the times shown in the SoA (Section 1.3).

Response Evaluation Criteria in Solid Tumors v1.1 (Eisenhauer et al. 2009) and iRECIST (Seymour et al. 2017) will be applied as the primary criteria for assessment of tumor response and date of tumor progression. The method of tumor assessment used at baseline must be used consistently throughout the study. Local tumor imaging (investigator assessment with site radiological reading) will be used. See Section 8.1.1 for detailed information regarding iRECIST for immune-based therapies.

Computed tomography (CT) scans, including spiral CT, are the preferred methods of measurement (CT scan thickness recommended to be ≤ 5 mm); however, magnetic resonance imaging is also acceptable in certain situations, such as when body scans are indicated or if there is a concern about radiation exposure associated with CT. Intravenous and oral contrast are required unless medically contraindicated.

See Section 9.4.3 for definitions of the efficacy endpoints.

8.1.1. iRECIST for Immune-Based Therapies

Rationale of Using iRECIST after First Radiologic PD by RECIST 1.1

The response to immunotherapy may differ from the typical responses observed with cytotoxic chemotherapy, including the following (Wolchock et al. 2009; Nishino et al. 2013):

- Response to immunotherapy may be delayed.
- Response to immunotherapy may occur after progressive disease by conventional criteria.
- The appearance of new lesions may not represent progressive disease with immunotherapy.

Therefore, to adequately characterize additional patterns of response and progression specific to patients treated with immunotherapy, which cannot be captured using conventional criteria such as RECIST v1.1, alternative measures of tumor assessment have been developed. The iRECIST standard was developed by the RECIST working group for the use of modified RECIST version 1.1 in cancer immunotherapy trials (Seymour et al. 2017).

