After initial disease progression defined by RECIST 1.1, iRECIST guidelines will be applied in the following tumor assessments. In iRECIST, any new lesions are categorized as measurable or non-measurable. Up to 5 lesions total (up to 2 per organ) can be selected as new lesion-target (NL-T). All other new lesions will be followed as new lesion-non-target (NL-NT). The NL-T sum of diameters will be calculated and recorded separately from the sum of diameters for target lesions identified at baseline.

Tumor response by iRECIST will be classified as confirmed progression (iCPD), or unconfirmed progression (iUPD), or stable disease or response (iSD/iPR/iCR) at all subsequent imaging. The initial tumor scan showing disease progression by RECIST 1.1 will be assigned as unconfirmed progression (iUPD) for overall response.

Progression is considered confirmed (iCPD), if the previous response status was iUPD and any of the following happens:

- For target lesions: any further increase in the previously identified target lesion sum of diameters by 5mm or more after iUPD.
- For non-target lesions: any further increase in the size of previously identified non-target lesion iUPD (the increase doesn't need to meet RECIST 1.1 criteria for unequivocal progression)
- For new lesions:
 - an increase in the NL-T previously identified as iUPD and increase ≥ 5 mm in sum of diameter OR
 - any increase for NL-NT OR
 - any appearance of additional new lesions

The overall response remains iUPD, IF

- target lesions were the cause of the initial iUPD AND
- target lesions haven't worsened, but they are still above PD threshold (20% increase from the nadir), AND
- no above factors of iCPD occur.

When progression is considered not unconfirmed, the overall response can become iSD/iPR/iCR instead of iUPD if any of the following criteria are met:

- iCR: Target lesions and non-target lesions have regressed completely AND no new lesions.
- iPR: Target lesions have regressed to $\geq 30\%$ decrease from baseline (iCR or iPR) AND non-target lesions remain non-iCR/non-iUPD AND no new lesion
- iSD: Target lesions have regressed to $< 20\%$ increase from nadir AND non-target lesions remain non-iCR/non-iUPD AND no new lesion.

Imaging and Treatment Guideline for Patients Who Have Radiologic Evidence of Progressive Disease by RECIST 1.1

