5.4.8.1. Primary Efficacy Analyses

The **ORR** is defined as the number of patients who achieve a best overall response of CR or PR divided by the total number of patients treated (safety population). The ORR, with 95% CI, will be summarized for each study part. Per RECIST 1.1 criteria, ORR for the single arm treatment within each tumor type will be calculated by confirmed best responses. Therefore, best overall response will be determined from a sequence of response assessments. Two objective status determinations of CR before progression are required for a best response of CR. Two determinations of PR or better before progression, but not qualifying for a CR, are required for a best response of PR. In the case of SD, measurements must have met the SD criteria at least once after study entry at a minimum interval not less than 6 weeks \pm 7 days measured from study entry.

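### The SAP requires confirmed response for ORR but states no confirmation for iBOR, so a gap between iORR and ORR mixes unconfirmed responses with responses after iUPD

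*SAP*

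**What the plan says.** For ORR, SAP 5.4.8.1 states that "ORR for the single arm treatment within each tumor type will be calculated by confirmed best responses". It then gives the rule for each category: "Two objective status determinations of CR before progression are required for a best response of CR", and "Two determinations of PR or better before progression, but not qualifying for a CR, are required for a best response of PR". SAP 5.4.8.2 carries confirmation over to DCR and also builds it into the definition of TTR.

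For iORR, SAP 5.4.8.3 counts patients whose iBOR is iCR or iPR, and adds that "iBOR is defined as the best response across all time point assessments based on RECIST 1.1 and iRECIST". It states no second determination and does not refer back to 5.4.8.1. The same section restricts iDoR to patients who are responders by iBOR.

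The denominators match: ORR is "divided by the total number of patients treated (safety population", and iORR is taken "out of all treated patients (safety population".

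Protocol 9.4.3.3 leaves the detail of the iRECIST endpoints to the SAP. Protocol 8.1.1 explains why iRECIST is used, "Response to immunotherapy may occur after progressive disease by conventional criteria", and when it starts to matter: "After initial disease progression defined by RECIST 1.1, iRECIST guidelines will be applied in the following tumor assessments".

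**The concern.** Up to the first RECIST 1.1 progression the two systems look at the same scans in the same way. iRECIST adds something only after that point. If the two response rates followed the same confirmation rule, any extra responder in iORR would be one whose response depended on a scan after iUPD.

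The stated rules differ in a second way. A patient with one PR, never repeated and before any progression, is a non-responder for ORR and a responder for iORR. SAP 5.4.8 reports both rates for each arm with exact 95% intervals, so a reader will naturally compare them, and the plan has no table that separates the two sources of a difference. Unconfirmed responses could then be taken for the delayed or post-progression responses that iRECIST was added to capture. iDoR inherits the same responder set, so it would also include patients who are not responders for DoR.

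**Working it through.** **Inputs from the documents.** ORR needs two determinations before progression (SAP 5.4.8.1). iBOR has no stated confirmation (SAP 5.4.8.3). Both denominators are the safety population. The combination cohort in each of TNBC and gastric adenocarcinoma is about 40 patients, and each monotherapy cohort is 8 (SAP 5.1.2 and 5.2.2). Intervals are Clopper-Pearson.

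**Inputs assumed, because the documents give neither.** p is the share of patients with a CR or PR at any time point, taken as 25% with a range of 10% to 40%. u is the share of those never confirmed, taken as 10% to 30%. To isolate the confirmation effect, responses after iUPD are set to zero.

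**The plan's own figures.** The documents state no iORR figure. Their only figures on the precision of a response rate are the ten intervals in SAP Table JZIA.5.1, and all ten reproduce to two decimals. For example, 10/40 gives 0.127 to 0.412 against the stated 0.13 to 0.41.

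**Step 1: what the gap contains.** With N treated patients, let
- U = patients with a single CR or PR before progression and no response after iUPD;
- P = patients with a response after iUPD and fewer than two determinations before first progression.

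As written, iORR − ORR = (U + P)/N. Only P depends on iRECIST.

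**Step 2: size of the U part, with P = 0.** The expected gap is p × u. The chance of at least one extra responder is 1 − (1 − p·u)^N. For N = 40 and p = 25%:

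| u | ORR | iORR | Gap (points) | Expected extra patients | Chance of any gap |
|---|---|---|---|---|---|
| 10% | 22.5% | 25% | 2.5 | 1.0 | 0.64 |
| 20% | 20.0% | 25% | 5.0 | 2.0 | 0.87 |
| 30% | 17.5% | 25% | 7.5 | 3.0 | 0.96 |

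Over p = 10% to 40% and u = 10% to 30%, the expected gap is 1.0 to 12.0 points. The chance of any gap is 0.33 to 0.99 at N = 40 and 0.08 to 0.64 at N = 8. If u = 0 the gap is zero.

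**Step 3: an example with and without a matched rule.** Take 40 patients with 10 confirmed responders, 3 unconfirmed responders and no response after iUPD. As written, ORR is 10/40 = 25.0% (12.7% to 41.2%) and iORR is 13/40 = 32.5% (18.6% to 49.1%). With two determinations required for both, each is 25.0% and the gap disappears.

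**The case against.** **The SAP is silent; it does not say that unconfirmed responses count.** Since iBOR is partly based on RECIST 1.1, and this SAP uses confirmed best response under RECIST 1.1, the rule might be meant to carry over. The abbreviation note under the first-progression table in Protocol 8.1.1 also describes iCR as confirmed. This weakens the charge but does not remove it. That note describes iSD the same way and does not list iPR. The main abbreviation list (Protocol Appendix 7) and the note to SAP Table JZIA.5.3 do not call iCR or iPR confirmed. The SAP states confirmation for ORR, DCR and TTR, so its absence here would reasonably be programmed as written.

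**A reader might infer that iORR must exceed ORR by construction.** It need not. The rates are equal when every response is confirmed and none follows iUPD. Moreover, iORR could not fall below ORR even with matched rules, because it keeps the RECIST 1.1 assessments and adds later ones. The defect is the mixed source of the gap, not its sign.

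**A reader might also infer that iORR cannot show immune-type responses.** The documents do not support that. Responses after iUPD are defined in Protocol 8.1.1 and are counted in iORR. Deriving iPFS under Table JZIA.5.3 already requires identifying patients whose iUPD is followed by stable disease or response. What is missing is a planned tabulation of such responders.

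**The stakes are limited.** No analysis of the difference is planned, iORR is exploratory, and SAP 5.2.1 rules out formal testing of response rate. One to three patients is also small beside an interval of 0.13 to 0.41 at 10/40. All of this stands, and it sets the weight of the point.

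**Conclusion.** The point holds as a mismatch of stated rules: ORR requires confirmation and iBOR, as written, does not. Any gap between iORR and ORR therefore combines unconfirmed RECIST 1.1 responses with responses after iUPD, and it cannot by itself be taken as evidence of immune-type activity. The iDoR population is affected in the same way, although the documents give no basis for a size there.

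The 1 to 3 patients in 40 (2.5 to 7.5 points) rest on an assumed 25% time-point response rate, an assumed 10% to 30% never confirmed, and no responses after iUPD. The size moves directly with those inputs and vanishes if every response is confirmed.

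This is a cheap improvement to an exploratory endpoint. It affects interpretation only and touches no primary objective or planned test.

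**What to change.** In SAP 5.4.8.3:

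1. When deriving iBOR, require two determinations of iCR, or of iPR or better, before confirmed progression (iCPD), allowing an intervening iUPD that is not confirmed. The wording of 5.4.8.1 should not be copied unchanged. Its condition that both determinations precede progression would, if read as first RECIST 1.1 progression, exclude the responses that iRECIST is there to capture.
2. Use the same responder set for iDoR.
3. Add a row giving the number of responders whose response came after iUPD, meaning those who needed at least one determination after an iUPD to qualify. Under the matched rule a patient with fewer than two determinations before first progression can qualify only in this way, so the row accounts for the whole gap between iORR and ORR.

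The cost is a sentence or two of SAP text, one table row and a slightly less favourable iORR. No new data are needed. If confirmation was always intended, the change only records it before analysis.

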If a patient is clinically stable at the first radiologic PD by RECIST 1.1, the patient should not be discontinued from the study until progression is confirmed no less than 4 weeks and no more than 8 weeks later by iRECIST. The continuation of treatment after initial radiologic PD takes into consideration the observation that some patients may experience transient tumor flare or pseudoprogression with immunotherapy, but could have disease response later. Patients who receive confirmatory imaging do not need to undergo the next scheduled tumor imaging if it is less than 4 weeks later; tumor assessment will resume at the next scheduled imaging time point, if clinically stable. Patients will be discontinued from study treatment if disease progression is confirmed by iRECIST (Seymour et al. 2017).

If a patient is clinically unstable, the patient should be discontinued from the study treatment at the first radiological PD by RECIST 1.1. The repeat tumor imaging for confirmation of PD by iRECIST is not required.

Clinical stability is defined as the following (Seymour et al. 2017): no worsening of performance status; absence of signs or symptoms that are associated with clinically significant disease progression; no requirement for intensified management, including increased analgesia, radiotherapy, or other palliative care. Clinical stability is ultimately defined by the treating investigator.

A summary of imaging and treatment guidelines for patients who have first radiologic PD is listed in the table below.

Imaging and Treatment Guideline for Patients who have First Radiologic PD by RECIST 1.1

	Clinically Stable		Clinically Unstable	
	Imaging	Treatment	Imaging	Treatment
First radiologic evidence of progressive disease by RECIST 1.1	Repeat imaging at 4 to 8 weeks to confirm PD by iRECIST	May continue study treatment while waiting for confirmatory scan by iRECIST	Not required; Repeat imaging at 4 to 8 weeks to confirm PD per investigator's discretion only	Discontinue treatment
Repeat tumor imaging confirms PD (iCPD) by iRECIST	No additional imaging required	Discontinue treatment	No additional imaging required	Not applicable
Repeat tumor imaging shows iUPD by iRECIST	Repeat imaging at 4 to 8 weeks to confirm PD by iRECIST. May occur at next regularly scheduled imaging visit	Continue treatment at the investigator's discretion	Repeat imaging at 4 to 8 weeks to confirm PD per investigator's discretion only	Discontinue treatment.

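### SAP Table JZIA.5.3 gives two answers for an iUPD followed by a late death or late confirmation, and states no precedence between its event rows and its gap-censoring row

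*SAP*

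**What the plan says.** Rows of SAP Table JZIA.5.3 (section 5.4.8.3) are counted from the top.

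- Row 1, "iUPD confirmed at next assessment (iCPD) or consecutive iUPD followed by an iCPD": event at the first iUPD date, with no time limit on the confirmation.
- Row 2, only further iUPDs and then no more scans: event at the first of them.
- Row 3, "iUPD without subsequent assessment": event at the iUPD date.
- Row 4, death: "Death date if no iUPD date as in the above 3 situations before death". The definition in the text agrees, since death counts there only when no progression came first.
- Row 5: no death and no iUPD, or an iUPD reset by iSD, iPR or iCR: censored at the last adequate assessment.
- Row 6, "Confirmed iUPD (iCPD) or death reported after 2 scan intervals following the last adequate tumor scan": censored, at "Date of last adequate tumor scan prior to confirmed iUPD (iCPD) or death".

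Footnote b lists iUPD among the results that make a scan adequate. Footnote c, which is in the SAP, sends the reader to the SAP for the length of 2 scan intervals; no definition is given. The same footnote mentions "new anticancer therapy in SAP", but the table has no row for new therapy. iDoR follows the same scheme.

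The iPFS start "should be the date of randomization (the date of first dose for single-arm study"), whereas PFS in section 5.4.8.2 runs from start of treatment.

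For clinically unstable patients, Protocol 8.1.1 states: "The repeat tumor imaging for confirmation of PD by iRECIST is not required". In the post-treatment schedule (Protocol 1.3), imaging continues only for patients who stop without objectively measured progression, while survival is collected until death, withdrawal or loss to follow-up.

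**The concern.** One patient can meet row 6 and also row 1 or row 3. Because the iUPD scan is itself adequate, row 6 can place the censoring on the very date that rows 1 and 3 make the event date. If row 6 is coded as an override, further evidence of progression (a death, or a late confirming scan) turns an event into a censoring, while the same iUPD with nothing after it stays an event.

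Two programmers could code the table differently and both claim to follow it. Under the override, more iPFS events would become censorings as deaths accrue, and the curve would rise. The first RECIST 1.1 progression scan is by definition the iUPD scan (Protocol 8.1.1). So such a patient would ordinarily be a PFS event and an iPFS censoring on the same date, and iPFS could exceed PFS with no pseudoprogression behind it.

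**Working it through.** The documents give no sample size, event count or precision figure for iPFS, so there is no stated figure to reproduce. The check applies the table's rows to hypothetical patients.

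**Inputs.** Scans are every 6 weeks ± 7 days to week 36 (Protocol 1.3). Two scan intervals are assumed to be 2 × 6 = 12 weeks, or 13 weeks with one 7-day window; results are the same at both. Confirmation is planned 4 to 8 weeks after the first progression (Protocol 8.1.1). An iUPD scan is adequate (footnote b).

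**Two readings of row 6.** Reading 1 measures the gap up to the iCPD scan or death. Reading 2 treats the confirmation limb as a missed-scan rule and measures the gap up to the iUPD that is later confirmed. Death is handled alike in both.

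Cases A to E have iSD at week 6 and iUPD at week 12. E = event, C = censored, followed by the week.

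| Case | Rows 1–4 prevail | Row 6 prevails, reading 1 | Row 6 prevails, reading 2 | After the fix below |
|---|---|---|---|---|
| A: nothing after | E 12 | E 12 | E 12 | E 12 |
| B: iCPD week 18 (gap 6) | E 12 | E 12 | E 12 | E 12 |
| C: iCPD week 26 (gap 14) | E 12 | C 12 | E 12 | E 12 |
| D: death week 20, no scan (gap 8) | E 12 | E 12 | E 12 | E 12 |
| E: death week 28, no scan (gap 16) | E 12 | C 12 | C 12 | E 12 |
| F: iSD week 6, iUPD week 24 (gap 18), iCPD week 30 | E 24 | E 24 | C 6 | C 6 |
| G: as F, nothing after the iUPD | E 24 | E 24 | E 24 | C 6 |
| H: iSD week 6, death week 28 (gap 22), no iUPD | E 28 | C 6 | C 6 | C 6 |

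When row 6 prevails, both readings censor a better-documented progression and keep a less-documented one as an event: C and E against A under reading 1, E against A and F against G under reading 2.

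**Can rows 1–4 simply be taken to win?** Then row 6 would never act, because row 4 already makes every death without a qualifying iUPD an event and row 1 already covers every confirmed iUPD. Row 6 must override something, and the table does not say what. In Table JZIA.5.2 the parallel rule sits under the word *Unless*, so its override is explicit.

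**Illustration of size.** Assume exponential iPFS with a true median of 12 weeks, and recode a share f of events as censorings on the same date, independently of time. The estimated hazard becomes (1 − f) × ln 2 / 12, so the median becomes 12 / (1 − f).

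| f | Events left of 40 | 12 / (1 − f), weeks | Simulated Kaplan-Meier median, n = 40, 4000 runs |
|---|---|---|---|
| 0.1 | 36 | 13.3 | 13.3 |
| 0.2 | 32 | 15.0 | 15.0 |
| 0.3 | 28 | 17.1 | 17.1 |
| 0.4 | 24 | 20.0 | 20.0 |

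At f = 0 the simulated median was 11.5 against the true 12. The values of f are assumptions.

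**The case against.** The strongest answer is that the table already settles late death. Row 3 makes the unrescanned iUPD an event, row 4 puts a qualifying iUPD ahead of death, and the text definition says the same. On that view, row 6's death limb reaches only deaths with no prior iUPD (case H), a deliberate missed-assessment rule like the one for PFS. This is a fair reading, and it is the one the fix would write down. It does not remove the conflict: row 6 as worded is not limited to such deaths, and nothing ranks it against rows 1 to 4.

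Late confirmation is the weaker limb. It conflicts with rows 1 and 3 in this way only under reading 1, and it needs a scan well outside the 4-to-8-week window.

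The size also invites overstatement. A reader might multiply an assumed unrescanned share of 30% to 70% by survival beyond 12 weeks after iUPD. Medians of 16 and 26 weeks give 0.5^(12/16) = 0.595 and 0.5^(12/26) = 0.726, hence 0.3 × 0.595 = 18% up to 0.7 × 0.726 = 51% of events lost. With an assumed 8-week median, which may suit clinically unstable patients better, 0.5^(12/8) = 0.354 and the range is 11% to 25%. No document supplies a rescan share or post-progression survival, and every figure requires row 6 to prevail and the deaths to be observed before cut-off.

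The missing new-therapy row is not in itself an error, since not censoring at new therapy is a legitimate estimand choice. What stands is that footnote c points to a rule the table lacks. The mixed time origin is minor and its effect is unquantified.

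**Conclusion.** The table is internally inconsistent and must be settled before iPFS is programmed. For an iUPD followed, with no further scan, by death more than 2 scan intervals later, it supports both an event and a censoring on the same date. This route is foreseeable from Protocol 8.1.1 and 1.3; its frequency is not known. Late iCPD raises the same conflict but should be rare.

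If row 6 overrides, iPFS and iDoR are biased upward. The size cannot be derived from the documents; the 13-to-20-week medians above are an illustration resting on assumed shares of 10% to 40% and an assumed 12-week true median.

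Two stronger inferences are not supported. One is that the table definitely censors these patients: rows 1, 3 and 4 and the text definition say otherwise. The other is that any iPFS longer than PFS would be an artefact: row 5 keeps a patient at risk when an iUPD is followed by iSD, iPR or iCR, so real pseudoprogression also lengthens iPFS. The consequence is confined to exploratory endpoints.

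**What to change.** Amend SAP section 5.4.8.3 and Table JZIA.5.3 as follows.

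1. **Precedence.** Once an iUPD has occurred and has not been reset by iSD, iPR or iCR, its first date is the event date, whatever follows.
2. **Gap row.** Apply row 6 only to a first iUPD (whether or not later confirmed) or a death that itself ends a gap of more than 2 scan intervals, with no unreset iUPD before it. This gives the last column of the case table: A to E agree with one another, and so do F and G.
3. **2 scan intervals.** Define the length in the SAP, covering the 6-week and 9-week schedules and any window allowance.
4. **Origin.** Use date of first dose for all patients, as PFS does. D1 and D2 each mix 8 randomised Stage 1 patients with about 32 non-randomised Stage 2 patients.
5. **New therapy.** Reconcile footnote c with the table: either add a row or delete the mention.

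This is a text edit and needs no new data. iPFS may look slightly less favourable than if row 6 overrode the iUPD rows. In the other direction, an unconfirmed iUPD after a long gap (case G) becomes a censoring. The choice should be fixed before iPFS results are seen.
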